#### **INNOVATION**

- (1) The proposed exercise paradigm represents a shift from general exercise prescriptions to a clinically feasible, rigorous individually tailored approach. Baseline CPX testing is used to inform the participant's exercise prescription based on heart rate range (HRR) rather than exercise type, thus controlling for exercise intensity. Data from our preliminary work and Pernow show that the threshold for NPY release during exercise is strongly correlated with the anaerobic threshold and occurs at a *mean* of 75% of  $VO_2$  max.

Progressively targeting individually determined HRRs to eventually reach the anaerobic threshold associated with NPY release will increase the likelihood that NPY synthesis and release will be upregulated across training. Using HRR as the exercise target also allows participants to choose their preferred exercise type (i.e. walking, running, cycling or swimming) and may increase the likelihood of long-term exercise maintenance. (2) Restoring or increasing the capacity to release NPY during stress through exercise is a novel PTSD and CP treatment approach, as well as a novel means to increase the likelihood of exercise maintenance via effects on capacities for reward and self-regulation.

(3) Integrating biological and neuropsychological constructs to improve therapies for the complex CP/PTSD population is novel and more likely to reduce disability and negative health consequences in the long-term.

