**Cold Pressor Test (CPT):** Per standard CPT procedures, participants will hold their right hand, up to the wrist, in a temperature controlled ice water bath, while keeping the hand still. They are instructed to say when they first experience pain and to withdraw their hand when the pain becomes intolerable. Pain threshold is defined as the number of seconds between hand immersion and the first report of "pain." Pain tolerance is defined as the number of seconds between hand immersion and hand withdrawal from the water. To prevent risk to subjects, a 7-minute time limit for immersion, unknown to the patient, is imposed. The CPT is performed just before and 30' after CPX testing to assess effects of acute exercise on pain sensitivity. To assess effects of exercise training on resting pain sensitivity, the CPT also will be performed 1-

2 days before each CPX and at the exercise-training midpoint. At these sessions, participants will engage in the same procedures (except the CPX) at the same time of day as those performed at the CPX sessions.

**Progressive Exercise Training Program:** After the initial CPX and CPT sessions, participants return to the CSU for 2 exercise-training sessions with our exercise physiologist. A pre-programmed heart rate monitor that “beeps” when exercise intensity increases is provided to participants to ensure that the targeted HRR is reached in accordance with individualized progressive exercise prescriptions. After these sessions, the exercise physiologist will instruct participants to gradually increase the frequency of their prescribed exercise sessions at home (per protocol) to 3x/week by week 4. During weeks 4, 7, and 10 an investigator will call participants to check-in and discuss any barriers to exercise. Basic motivational interviewing techniques (i.e. reflective listening) and problem solving strategies (the current standard of care in this area) will be used to facilitate exercise compliance while maintaining safety. To verify home exercise, participants will wear an actigraph and heart rate monitor that measures activity and heart rate. Data from the heart rate monitor will be downloaded and reviewed with participants upon return to the clinic for test sessions.

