### Statistical Analysis Plan

**Power and Sample Size Considerations:** Power calculations were carried out based on our recently published study which measured NPY, at baseline and peak time-points, in response to a single cardiopulmonary exercise stress test (CPX). Achievement of a Cohen’s d effect size of .5 will suggest statistically and clinically significant effects of the treatment within the CP/PTSD group. Thus, in order to obtain a power of 80% at the 5% level of significance a sample size of 30 participants will be required.

**Data Analyses:** Baseline demographics and descriptive variables (e.g., age, gender, pain duration) will be summarized. Descriptive summaries for continuous variables will be presented in terms of means and standard deviations while discrete variables will be summarized in terms of relative frequencies and percentages.

**Aims 1-2 &4:** The hypotheses under Aims 1, 2 and 4 will be evaluated using unconditional latent growth models (LGMs). The approach does not assume a linear trajectory and is thus ideal for this proposal. The intercept of the LGM will be centered on the baseline self-report data (i.e., first slope loading will be fixed to 0.0). The intermittent time point (midpoint) will be freely estimated, and the final post-training time point will have a corresponding slope factor loading fixed to 1.0. Accordingly, the mean and variance of the slope factor will convey the fixed (average) and random effects (individual differences) of change across exercise training. Effects of the exercise program will be evidenced by a significant slope factor mean (indicating significant change in the metric of interest). A significant slope variance will indicate individual differences in change across training and support further investigation of predictors of the variability.

**Aim 3:** At both CPX testing time-points, the putative mechanisms under investigation (reward, self-regulation, exercise-based SE and IM) will be correlated with each other using Pearson or Spearman correlations, as appropriate. Based on these findings, these putative psychological mechanisms will be entered as predictors in a discriminant function analysis to predict exercise maintenance.

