**Feasibility to achieve AIMS:** Recruiting veterans can be challenging, but inclusion of non-veterans allows us to successfully carry out our studies in this area. To enhance recruitment, we both advertise and work with collaborators at affiliated institutions who refer participants. Finally, we have an experienced multidisciplinary team and infrastructure in place, which is critical to the success of our studies in this area. In [name] CDA2 study to date, there have been no dropouts once subjects begin exercise.

**Additional Considerations:** Some participants may not respond to exercise training which could spur the development of novel pharmacological approaches to address a possible inability to increase the release of NPY in response to exercise. We will collect and process additional blood at each session to enable measurement of additional relevant biomarkers of interest (e.g., neurosteroids, ACTH, inflammatory markers) as possible with additional funding by the NC-PTSD or other funding sources.

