- (b) In-person screening evaluation: Demographics and self-report symptom questionnaires will be administered; the latter will provide information regarding trauma history and PTSD, depressive and other psychiatric symptoms. All information from these questionnaires will be identified with participant codes only. Structured diagnostic interviews will be completed by the study PI to confirm trauma history, PTSD diagnosis, risk to self/others, other psychopathology, substance use and ability as well as willingness to abstain from neuroactive substances or substances that might affect levels of the neurobiological factors to be assayed. All information from these interviews will be identified with participant code only. A Certificate of Confidentiality will be obtained from the NIMH to protect participants from potential legal demands for study data. Data from these interviews and questionnaires will be entered into the database and securely stored as noted above. Clinical interviews will be audio-recorded to determine diagnostic reliability only after obtaining appropriate consent. These digitized audio-recordings will be identified with participant codes only and stored on a secure folder on a secured server, with access restricted to approved staff, as described above. These audio-files, which may inadvertently divulge PHI (e.g. voice), will be stored on a separate server than the self-report, diagnostic interview, and other data without PHI. Potential medical issues requiring medical attention will be discussed by the PI with the study MD/Co-I, [name], as well as with the participant, and the participant will be referred to the participant's health provider as appropriate. Participants receiving

care outside of the VA will have to sign a consent for release of such information if direct communication between the research personnel and outside provider is desired.

- (c) The symptom limited CPX sessions will be conducted in the VABHS Clinical Studies Unit (CSU) exercise physiology laboratory by qualified clinical- and research-credentialed staff. Participants will also perform exercise training sessions (per protocol) at the CSU with supervision by an exercise physiologist with available medical support should any safety issues arise. Data from these sessions (including actigraph and heart rate data) will be coded and stored using protections described above.

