**7. Potential coercion:** We expect that any risks of coercion will be low. First, participants who do not wish to participate in the study or who wish to drop out of the study after enrollment will not experience any negative consequences and will be referred to VA or community-based treatment for CP/PTSD if desired. Second, potential participants will initiate contact with study staff if they are interested, which reduces coercion. A potential human subjects concern is whether the financial compensation offered is too high and therefore coercive to participants. We believe the rate of compensation for the current study is fair and matched to time needed to complete procedures and any additional inconveniences. Travel is compensated to address a potential disincentive to study participation. Participants will be compensated for most study sessions based on the time required—as payment may be needed to offset babysitting costs or time away from work. We plan to pay at rates commensurate with time spent (~\$20 an hour), which is the standard at VABHS. Specifically, participants will be compensated \$90 for participation in the full screening evaluation, \$50 for participation in each CPT session (3 total), \$50 for participation in each CPX testing session (2 total), \$25 for in clinic exercise training sessions (up to 10 total) and \$10 for each home exercise session (26-31 total), \$5.00 for each telephone call (during weeks 3 through 12 while he/she is exercising at home (up to 10 total)), and \$20 for each follow-up phone call (1-month and 3-month). If the participant participates in all of the study procedures over the ~6 month study, he/she will be compensated up to \$990.00. Finally, all study procedures will be fully explained during the informed consent process such that participants can make an informed decision regarding their level of commitment and willingness to engage in study procedures given the risks. In addition, participants will be informed and reminded that they are free to withdraw from the study at any point without forfeiting payment for any procedures in which they have already participated.

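### Home-training records are collected but enter no planned analysis, so associations between NPY change and outcome change may partly reflect how much each participant trained

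*Combined protocol and SAP*

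**What the plan says.** **Training and its record.** The Progressive Exercise Training Program paragraph gives 2 clinic sessions, after which participants "gradually increase the frequency of their prescribed exercise sessions at home (per protocol) to 3x/week by week 4". The payment paragraph under Psychological risks lists 26 to 31 paid home sessions and up to 10 clinic sessions. The monitoring is stated plainly: "To verify home exercise, participants will wear an actigraph and heart rate monitor that measures activity and heart rate".

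**Use of the record.** Two uses are given. One is feedback: "Data from the heart rate monitor will be downloaded and reviewed with participants upon return to the clinic for test sessions". The other is storage, in section 8.1 b: "Data from these sessions (including actigraph and heart rate data) will be coded and stored using protections described above".

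**Analysis.** The hypotheses under Aims 1, 2 and 4 "will be evaluated using unconditional latent growth models (LGMs"). Aim 3 uses correlations among psychological measures, then a discriminant analysis on those measures. No session count, time in range, actigraphy or other training variable is named. The one opening is that a significant slope variance would support looking for predictors of it; none is listed.

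**Role of intensity.** The Innovation section makes training intensity part of the mechanism: "Progressively targeting individually determined HRRs to eventually reach the anaerobic threshold associated with NPY release" is expected to make upregulation of NPY more likely.

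**Non-response.** Under Additional Considerations: "Some participants may not respond to exercise training which could spur the development of novel pharmacological approaches", directed at a possible inability to release more NPY. Training received is not mentioned there.

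**The concern.** Hypotheses 1b, 2b and 4b are between-person associations of change in a single trained group. A participant who trains more could plausibly gain more NPY release and, separately, more self-efficacy, motivation and symptom relief. The two changes would then correlate even if NPY did nothing. The protocol expects uneven compliance, since it schedules calls about barriers to exercise. Its report of no dropouts in the ongoing study describes retention, not training done.

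At stake is the mechanistic reading. The Significance section treats NPY augmentation as a possible mediator of benefit, and the Summary of Significance proposes calibrating exercise programmes to NPY. A flat NPY response might likewise reflect too little training at the needed intensity, and nothing planned would show that. The baseline hypotheses (1a, 2a, 4a) are not affected.

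**Working it through.** **1. The plan's own figure.** N = 30 is given for a within-group d of .5, 80% power and the 5% level. Two-sided paired normal approximation: ((1.960 + 0.842)/0.5)² = 31.4, so 32, close to 30. The exact t calculation gives 34, with 75.4% power at 30. This figure concerns a mean change; the point here does not depend on it.

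**2. Share of training at home.** From the payment paragraph, at least 26/(26 + 10) = 72% of sessions. With 2 clinic sessions instead of 10 the share is higher.

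**3. Training as a shared cause.** Assumption: training correlates a with NPY change and with outcome change, and the two have no other link. The documents give no value for a, so a range is shown. The population correlation between the two changes is a × a. Approximate rejection rate at n = 30, two-sided 5%: Φ(√27 · atanh(a²) − 1.96), plus a negligible lower tail. For a = .5: atanh(.25) = 0.255; × 5.196 = 1.327; Φ(−0.633) ≈ 26%. Simulation (100,000 replicates), including a partial correlation adjusted for training measured with reliability .8:

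| a | a² | Unadjusted test rejects | Adjusted, reliability .8 |
|---|---|---|---|
| .3 | .09 | 7.6% | 5.2% |
| .4 | .16 | 13.5% | 5.4% |
| .5 | .25 | 27% | 6.2% |
| .6 | .36 | 51% | 8.3% |
| .7 | .49 | 81% | 13.4% |

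With training measured without error, the adjusted test rejects 5% throughout.

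**4. When adjustment costs power.** Assume training acts on the outcome only through NPY, with an NPY–outcome correlation of .5. If training correlates .5 with NPY change, the partial correlation is (.5 − .5 × .25)/√(.75 × .9375) = .45, and power falls from 83% to 70%. At .6 it is (.5 − .6 × .30)/√(.64 × .91) = .42, and power falls to 64%.

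**5. When adjustment misleads.** Assume NPY change and motivation change are unrelated but both drive training, each at .5. The unadjusted test rejects 5%. The partial correlation is −.25/(1 − .25) = −.33, and the adjusted test rejects 43%. At .4 it is −.16/.84 = −.19, with 17% rejection.

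**6. Cost of one covariate.** The critical |r| at n = 30 moves from .361 to .367, and the correlation detectable with 80% power from .492 to .500.

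**The case against.** Several points on the other side stand.

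- A reader might infer that the hypotheses would be falsely confirmed. They say only that changes will correlate. A shared training cause produces a real correlation, so rejecting zero is right for the hypothesis as worded; the error would be reading it as specific to NPY.
- A reader might infer that training and NPY effects cannot be separated. That goes too far. The records are kept, and the plan leaves room for unnamed predictors of slope variance. What is missing is a pre-specified analysis.
- A reader might infer a planned non-responder conclusion. There is none: one hedged sentence, with no definition, classification or analysis behind it.
- The test simulated is a correlation of two change scores. The plan names growth models judged by slope mean and variance, and does not say how NPY change is to be related to outcome change. The rates illustrate the exposure; they are not operating characteristics of the planned models.
- The beeping monitor, the barrier calls, per-session payment and clinic sessions should all narrow variation in training. That makes the higher values of a less certain, and at a = .3 the excess is small.
- Adjustment is not simply conservative. The protocol's own theory has motivation and self-efficacy sustaining exercise, and steps 4 and 5 show that adjusting can lose power or create bias.

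These points limit the strength of the claim and the form of the remedy. They do not supply a use for the records.

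**Conclusion.** The concern holds as a gap that is cheap to close. Training is recorded but not analysed, so the planned results would not show whether an NPY–outcome change association goes beyond training done, or whether a flat NPY response followed adequate training. The size is unknown. Under assumed training correlations of .3 to .6 and no NPY link, a 5% correlation test at n = 30 rejects about 8% to 51% of the time, with correlations of .09 to .36. These figures depend wholly on the assumed values. The documents do not support saying that the hypotheses would be wrongly confirmed, that the effects are inseparable, or that the plan draws a conclusion about non-responders.

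**What to change.** Before analysis, amend the Statistical Analysis Plan as follows.

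1. Pre-define one adherence variable from the monitor data: sessions completed, or minutes in the participant's prescribed HRR range over weeks 1–12. Use minutes above the CPX threshold only as a secondary description, because they mix adherence with baseline physiology and with the prescribed intensity range.
2. Summarise that variable for all participants.
3. Keep the unadjusted 1b, 2b and 4b associations as planned. Beside each, report a labelled sensitivity analysis adjusted for adherence, with estimates and confidence intervals.
4. State that an association which vanishes on adjustment will not be claimed as NPY-specific. State also that adjustment can mislead if training lies on the pathway or is itself driven by NPY and motivation, so the adjusted result does not replace the unadjusted one.
5. Report any NPY non-response alongside training received before suggesting biological inability.
6. Reconcile the training paragraph (2 clinic sessions; calls in weeks 4, 7 and 10) with the payment paragraph (up to 10 clinic sessions; up to 10 calls in weeks 3 to 12) before setting any prescribed-session denominator.

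No new visits or measurements are needed. The cost is some data processing, one degree of freedom, and lower power in the adjusted analysis if training acts through NPY (about 83% to 64–70% under the assumptions in step 4 of the working).

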### Statistical Analysis Plan

**Power and Sample Size Considerations:** Power calculations were carried out based on our recently published study which measured NPY, at baseline and peak time-points, in response to a single cardiopulmonary exercise stress test (CPX). Achievement of a Cohen’s d effect size of .5 will suggest statistically and clinically significant effects of the treatment within the CP/PTSD group. Thus, in order to obtain a power of 80% at the 5% level of significance a sample size of 30 participants will be required.

**Data Analyses:** Baseline demographics and descriptive variables (e.g., age, gender, pain duration) will be summarized. Descriptive summaries for continuous variables will be presented in terms of means and standard deviations while discrete variables will be summarized in terms of relative frequencies and percentages.

**Aims 1-2 &4:** The hypotheses under Aims 1, 2 and 4 will be evaluated using unconditional latent growth models (LGMs). The approach does not assume a linear trajectory and is thus ideal for this proposal. The intercept of the LGM will be centered on the baseline self-report data (i.e., first slope loading will be fixed to 0.0). The intermittent time point (midpoint) will be freely estimated, and the final post-training time point will have a corresponding slope factor loading fixed to 1.0. Accordingly, the mean and variance of the slope factor will convey the fixed (average) and random effects (individual differences) of change across exercise training. Effects of the exercise program will be evidenced by a significant slope factor mean (indicating significant change in the metric of interest). A significant slope variance will indicate individual differences in change across training and support further investigation of predictors of the variability.

**Aim 3:** At both CPX testing time-points, the putative mechanisms under investigation (reward, self-regulation, exercise-based SE and IM) will be correlated with each other using Pearson or Spearman correlations, as appropriate. Based on these findings, these putative psychological mechanisms will be entered as predictors in a discriminant function analysis to predict exercise maintenance.

**Feasibility to achieve AIMS:** Recruiting veterans can be challenging, but inclusion of non-veterans allows us to successfully carry out our studies in this area. To enhance recruitment, we both advertise and work with collaborators at affiliated institutions who refer participants. Finally, we have an experienced multidisciplinary team and infrastructure in place, which is critical to the success of our studies in this area. In [name] CDA2 study to date, there have been no dropouts once subjects begin exercise.

**Additional Considerations:** Some participants may not respond to exercise training which could spur the development of novel pharmacological approaches to address a possible inability to increase the release of NPY in response to exercise. We will collect and process additional blood at each session to enable measurement of additional relevant biomarkers of interest (e.g., neurosteroids, ACTH, inflammatory markers) as possible with additional funding by the NC-PTSD or other funding sources.

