**[[contact]](mailto:[contact])**

**Statistical Plan on page 8**

## AIMS and HYPOTHESES

The assessment and treatment of chronic pain (CP) and Posttraumatic Stress Disorder (PTSD) are national priorities for the National Institute of Health (NIH) and the Veterans Health Administration (VHA) as we continue to see steep increases in the prevalence of these conditions among returning Veterans as well as relatively high rates of these conditions among civilians. Our laboratory has developed a rigorous, individually tailored, 3-month progressive exercise training program that appears to modify a key factor (neuropeptide Y: NPY) involved in the pathogenesis of CP and PTSD. Preliminary data suggest that progressive exercise-training induced changes in NPY system function were associated with improvements in PTSD, depression and pain-related interference and sensitivity, as well as intrinsic motivation to exercise. The proposed R21 will extend this research to examine the relationship between progressive exercise-training induced changes in NPY and the capacity for reward and self-regulation. These latter capacities are thought to be essential to intrinsic and extrinsic motivation and self-efficacy, which are known to promote long-term exercise maintenance, which is critical for long-term health maintenance. Findings from the study are therefore expected to inform development of more effective therapeutic interventions for CP/PTSD aimed at forestalling serious long-term disability and reliance on pharmacological interventions with high potential for abuse, dependence, and morbidity. In the proposed study, we will investigate the association between changes in key biological and neuropsychological factors induced by a rigorous, 3-month individually tailored, progressive exercise training program and achievement of exercise maintenance in a CP/PTSD population.

**Aim 1.** Evaluate whether changes in neuropeptide Y (NPY) system function correlate with changes in self-regulation and reward across the rigorous 3-month individually tailored, progressive exercise training program.

**Hypothesis 1a:** Pre-training resting plasma NPY levels will correlate with capacities for self-regulation and reward.

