**Hypothesis 1b:** Changes in resting plasma NPY levels and the release of NPY in response to standardized cardiopulmonary exercise testing (CPX) conducted before and after a 3-month progressive exercise-training program will correlate with improvements in self-regulation and reward sensitivity.

**Aim 2.** Evaluate whether changes in NPY correlate with changes in self-efficacy and intrinsic motivation for exercise in response to a rigorous 3-month individually tailored, exercise-training program.

**Hypothesis 2a:** At baseline, acute exercise-induced increases in plasma NPY during CPX will correlate with exercise-related self-efficacy and intrinsic motivation to exercise.

**Hypothesis 2b:** The release of NPY during CPX will increase in response to the 3-month exercise-training program and correlate with increases in self-efficacy and intrinsic motivation to exercise.

**Aim 3.** Determine whether capacities for self-regulation and reward sensitivity, as well as self-efficacy and intrinsic motivation for exercise change in response to the 3-month exercise-training program and predict exercise maintenance.

**Hypothesis 3:** At endpoint, the factors under investigation will significantly predict exercise maintenance.

**Aim 4.** Evaluate whether changes in NPY system function across the 3-month exercise-training program correlate with improvements in pain sensitivity and interference, as well as depressive and PTSD symptoms.

**Hypothesis 4a:** At baseline, CPX-induced increases in plasma NPY will not correlate with pain-related interference and sensitivity, depression or PTSD severity.

**Hypothesis 4b:** At endpoint, CPX-induced increases in plasma NPY will correlate with reductions in pain-related interference and sensitivity, as well as with reductions in depression and PTSD symptoms.

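### The growth models named for Aims 1, 2 and 4 report change in one measure at a time, so the six NPY correlation hypotheses have no specified association test

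*Combined protocol and SAP*

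**What the plan says.** Under AIMS and HYPOTHESES, Aims 1, 2 and 4 carry six hypotheses, all about how NPY relates to something else. Hypothesis 1a is typical: "Pre-training resting plasma NPY levels will correlate with capacities for self-regulation and reward". Hypothesis 1b concerns changes in NPY, resting and in response to "standardized cardiopulmonary exercise testing (CPX) conducted before and after a 3-month progressive exercise-training program". Hypothesis 4a predicts that a baseline correlation is absent.

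The Statistical Analysis Plan assigns one method to all six: "The hypotheses under Aims 1, 2 and 4 will be evaluated using unconditional latent growth models (LGMs". The intercept is set at the baseline self-report data, the first and last slope loadings are fixed at 0 and 1, and "The intermittent time point (midpoint) will be freely estimated". Two read-outs follow. On the mean: "Effects of the exercise program will be evidenced by a significant slope factor mean (indicating significant change in the metric of interest". On the variance: "A significant slope variance will indicate individual differences in change across training and support further investigation of predictors of the variability".

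The only correlations in the SAP are under Aim 3, where the psychological mechanisms "will be correlated with each other using Pearson or Spearman correlations, as appropriate". NPY is not among them. The sample size of 30 rests on a within-group Cohen's d: an "effect size of .5 will suggest statistically and clinically significant effects of the treatment within the CP/PTSD group".

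**The concern.** A slope mean says whether a measure moved on average. A slope variance says whether people differed in how far it moved. Neither says whether those who gained more NPY also gained more self-regulation, motivation or symptom relief, which is what Aims 1, 2 and 4 ask. The SAP could be followed exactly, give significant results for every measure, and leave the central question untested.

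Any NPY correlation later reported would use a statistic chosen after the data were available. It could not be read as a prespecified test. Hypothesis 4a has a further risk: with no criterion, a non-significant correlation in 30 people could be taken as evidence of no correlation.

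**Working it through.** **1. Hypotheses against read-outs.** The Preliminary Data section defines NPY release as the rise from resting to peak level during the cardiopulmonary exercise test (CPX). Occasions come from the schedule of measures under Approach, the Cold Pressor Test text (the midpoint session leaves out the CPX) and the payment list under Potential coercion (two CPX sessions). The schedule shows a blood sample at the midpoint, so resting NPY has three occasions. Go/No-Go appears only at the two CPX visits.

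| Hypothesis | Question | NPY occasions in training | What the SAP read-outs give |
|---|---|---|---|
| 1a | Resting NPY vs self-regulation and reward, baseline | Resting: 3 | No baseline association |
| 1b | Change in resting and released NPY vs improvement in the same outcomes | Resting: 3; released: 2 | Mean and spread of change, each measure alone |
| 2a | Released NPY vs exercise self-efficacy and motivation, baseline | 2 | No baseline association |
| 2b, first clause | Mean rise in released NPY | 2 | Right kind of read-out, but the model needs a midpoint |
| 2b, second clause | That rise vs rises in self-efficacy and motivation | 2 | No association |
| 4a | No baseline correlation of released NPY with pain, depression or PTSD | 2 | No baseline association |
| 4b | Endpoint released NPY vs symptom reductions | 2 | Mean and spread of symptom change only |

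**2. Why the read-outs cannot carry the association.** For one measure at three occasions, the data supply 3 means and 6 variances and covariances, 9 in all. The model has 9 parameters: 2 factor means, 2 factor variances, 1 factor covariance, 3 residual variances and 1 free loading. With loadings 0, λ and 1, the expected means are μI, μI + λμS and μI + μS. So μS is the post-training mean minus the baseline mean. The slope variance likewise depends only on that measure's own means and covariances. NPY enters neither quantity for an outcome. Reassigning the NPY values among participants would leave every outcome result unchanged. This holds by definition and needs no assumed effect size.

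**3. The plan's own sample size.** For a mean change with d = 0.5, n = ((1.960 + 0.842)/0.5)² = 31.4, rounded up to 32, and power at 30 is 78.2% (two-sided 5%, normal approximation). The paired t calculation gives n = 34 and 75.4% power at 30. One-sided versions give 25 (normal) and 27 (t). Sidedness is not stated. The stated 30 is close to the two-sided normal figure, so it is a calculation for a mean change, not for a correlation.

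**4. What N=30 gives for a correlation.** Fisher z with standard error 1/√(30 − 3) = 0.192; two-sided 5% and no multiplicity adjustment are assumed.
- Correlation detectable with 80% power: tanh(2.802 × 0.192) = 0.49.
- The documents assume no correlation for this study. Over an assumed range, power is about 36% at r = 0.3, 60% at 0.4, 81% at 0.5 and 95% at 0.6.
- 95% interval at an observed r of 0: tanh(±1.960 × 0.192) = −0.36 to 0.36.

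**The case against.** The best defence is that the SAP is under-described rather than incapable. Unconditional rules out external predictors but not a bivariate growth model, whose intercept and slope covariances are associations. That is true of the method. The text, however, speaks of a single metric, does not name NPY in the model, and interprets only a mean and a variance. A bivariate version with a free midpoint would still not fit released NPY or Go/No-Go.

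A second defence is the promised look at predictors of variability. It points towards association, but names no predictor, model or test, and variability in change cannot address baseline hypotheses 1a, 2a and 4a. A reader might infer that this step is allowed only after a significant slope variance; the wording says such a result supports it, not that it is required.

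The intent to correlate is plain elsewhere. The Inclusion/Exclusion Criteria want a wide NPY range for that purpose, and Preliminary Data reports NPY correlations from earlier participants. Neither gives a method for this study.

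Two stronger readings are tempting and not supported:
- *The choice of scale is wide open.* Counting every scheduled self-regulation and reward score, with EEfRT as one, gives 7 for Hypothesis 1a and 7 × 2 = 14 pairs for 1b. These are upper limits. Significance, section C ties self-regulation and NPY to Go/No-Go and commits to both components of reward. The measures list makes commission errors the main Go/No-Go score. On that reading 1a has about 4 scores: Go/No-Go, two TEPS sub-scales and EEfRT. Some ambiguity remains, because the schedule lists other scales under self-regulation.
- *Hypothesis 4b contradicts Aim 4.* 4b names its NPY measure, the endpoint exercise-induced rise. Aim 4 speaks more broadly of change across training. That calls for clarification only.

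This is also a small single-arm mechanism study in which simple or exploratory tests are acceptable. That bears on how the tests are labelled, not on whether they are specified.

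**Conclusion.** The concern holds. Six of the study's seven hypotheses, all but Hypothesis 3, have no specified test of the NPY association they state. It would go too far to say that Hypothesis 2b has no relevant analysis at all: its mean-increase clause suits a slope mean in kind, though released NPY lacks the third occasion. Resting NPY does have a midpoint sample and can be fitted.

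The conclusion rests on the SAP wording and on the algebra of the model it describes, not on any assumed effect. The power and interval figures are context for the repair and rest on the assumptions stated with them. They do not show that 30 participants is wrong for the purpose the plan gives, a within-group d of 0.5. Because the named analysis does not address the stated aims, this should be corrected before the NPY data are analysed.

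**What to change.** In the SAP paragraph for Aims 1, 2 and 4, state an association analysis for each hypothesis, run whatever the slope variance shows:

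- **1a, 2a, 4a:** baseline correlation of the NPY measure named in the hypothesis with each listed outcome, with 95% confidence interval. Write down the rule for Pearson or Spearman.
- **1b and 2b (second clause):** correlation, or baseline-adjusted regression, of pre-to-post NPY change with pre-to-post outcome change, with 95% interval.
- **4b:** the same form for symptom reductions, using the endpoint exercise-induced rise that 4b names. Say whether change in that release across training (Aim 4) is also tested.
- **2b (first clause):** paired pre-to-post change in NPY release, with 95% interval.
- **Scores:** Go/No-Go commission errors as the main self-regulation score, other scheduled scales as secondary; for reward, the TEPS sub-scales and EEfRT.
- **Multiplicity:** one stated rule, or label the correlations exploratory.
- **4a:** judge the interval against a stated bound. At N=30 a 95% interval cannot lie inside any bound narrower than about ±0.36, so non-significance alone should not count as support.
- **Growth model:** keep it to describe mean change in measures with three occasions; analyse released NPY and Go/No-Go as two-occasion measures.
- **Sample size:** state that 30 was justified for a within-group d of 0.5, and give the detectable correlation of about 0.49 with its assumptions.

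The cost is SAP wording and simple analyses of data already scheduled, with no extra participants or visits.
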